5.8. Determination of metabolomic profiles and gut microbiota

This project will employ a metabolic and metagenomic profiling approach (gut microbiota) using state-of-the-art analytical technologies to provide a deeper understanding of metabolic responses to dietary intervention (reduction of red/processed meat intake) in the context of a Mediterranean dietary pattern. Therefore, lipid profiling and a complete metabolomic and metagenomic analysis will be performed to investigate specific changes caused by the intervention compared to the control. The determinations will be made at the hospital (general biochemistry) as well as at the Institute of Nutrition and Food Technology (INYTA). Once the main determinations explained below have been carried out and with prior consent, the surplus samples with their corresponding code will be stored at -80°C in the Biobank of the Public Health System of Andalusia (BBSSPA), for future analyses related to the project, including aliquots with leukocytes for DNA extraction and erythrocytes for studies of antioxidant defense enzymes.

5.8.1. Lipid metabolism, endothelial function and inflammatory markers

Fasting venipuncture blood samples will be obtained at the beginning and end of follow-up: two 10 mL tubes of K2E EDTA, and two 10 mL tubes of serum separator gel. First, part of the sample will be processed in the hospital according to its own established protocols to obtain blood biochemistries for the blood lipid fractions: total cholesterol, LDL-C (primary outcome), HDL-C, non-HDLC, triglycerides, glucose, insulin, HbA1c and CRP.

The rest of the samples will be processed at INYTA to obtain plasma and stored (-80 °C) until they are processed for analysis. The new LC-MS will be used to determine a specific plasma fatty acid profile, including palmitic acid (primary outcome), among others. Other plasma biomarkers of endothelial function, such as ICAM-1, VCAM-1, ELAM-1, and MPO, will be determined using Luminex®'s xMAP technology and MULTIPLEX kits; as well as endothelin-1 and angiotensin II using ELISA kits. Inflammatory biomarkers in plasma will also be determined with Luminex® xMAP and HSTCMAG-28SK kits, including IL-6, IL-8/CXCL8, IL-10, IL-23, TNF- α , IFN- γ . ELISA kits will be used to quantify lipopolysaccharides (LPS) and LPS-binding lipoprotein (LBP).

5.8.2. Metabolomic determinations

Plasma metabolomic profiles will be determined in a non-targeted manner using an LC-MS platform, although targeted analyses will also be proposed to determine endogenous and

exogenous metabolites specifically related to cardiovascular risk and meat consumption (e.g., TMAO, etc.). Non-targeted approaches are used to simultaneously measure hundreds/thousands of metabolic traits that then allow a metabolic signature to be profiled. For metabolite extraction, plasma samples will be mixed with an organic solvent preparation for protein precipitation, cooled, centrifuged, and filtered before being analysed. During this step, quality control (QC) samples will be prepared by taking 10 µL aliquots from all samples. Additional QC samples will be collected from subgroups of each group for further fragmentation analysis. The analysis will be carried out using two different LC methods coupled to an Orbitrap Q-Exactive instrument operating in positive and negative ionization modes, respectively, in order to relatively separate and quantify plasma metabolites. Pre-processing of the raw data generated will include removal of non-significant information, alignment, filtering, QC titration, drift correction, and normalization of the intensity of each ion, and will be carried out using MD-DIAL, XCMS, or a combination of proprietary R-based codes. A final table will be obtained containing: 1) mass/load ratio (m/z , mass error ≤ 3 ppm); 2) retention time (RT, min) and 3) chromatographic peak area for each of the metabolites. Additional fragmentation data will be acquired to improve information on metabolites. From current public metabolomic databases and from our own collection, metabolites will be mapped based on their m/z signal and fragmentation data. Identification will be carried out using appropriate chemical standards where possible. The information will be reported following the method suggested by Summer et al.

5.8.3. Determination of the composition of the gut microbiota

It will be carried out by 16S rRNA analysis of the samples obtained and previously processed and stored at -80° C. DNA will be obtained from the stool sample using the QIAamp DNA stoolmimi kit (Qiagen, Barcelona, Spain) and the PureLink™ Microbiome DNA purification Kit (Invitrogen). The quality and quantity of the same will be checked spectrophotometrically (NanoDrop ND-100). The variable V3-V4 region of the 16S rRNA gene will be amplified using specific oligonucleotides, by PCR. A second amplification will then be performed using barcode oligonucleotides. The purified PCR product will be sequenced on illumina's MiSeq platform.

5.8.4. Statistical analysis of metabolomic and metagenomic data

A "Knowledge Discovery from Databases" (DCBD) process will be followed, which will consist of:

- Selection of variables of interest and groups of subjects for analysis.
- Identify distinct clinical feature sets that are grouped into particular individual groups (phenotypic sets) without regard to their microbiota/metabolomic background.
- Examine the response associated with the intervention in each individual identified phenotypic set.

- Identify metabolomic networks composed of DMRs and metabolites that interact with each other.
- Integration of all previously identified patterns into a multi-layered space using genetic algorithms. The idea of this final step is, once the interesting variables derived from each of the previous approaches (phenotype, microbiota and metabolomics) have been identified, to incorporate them all together for the construction of a predictive model that allows the classification of good and bad responders to treatment.

To this end, different statistical methodologies will be used to identify anomalies, groups or patterns of metabolites, including principal component analysis (PCA) for the initial clustering. To differentiate metabolite patterns between the intervention and control groups, before and after the intervention, a novel multivariate approach, orthogonal partial least squares multiblock analysis of variance (AMOPLS), will be used. The AMOPLS consists of the application of a core-based multiblock OPLS approach on the pure matrices and those augmented by the residues arising from the ANOVA decomposition of the design response matrix and provides, as a product, a global view of the important effects on the model, which allows its interpretation. Analysis of variance and/or linear regression will test the main effects of: 1) time (follow-up vs. baseline); 2) intervention group vs. control; 3) interaction time x intervention group. Univariate analyses will be used to compare baseline means between the intervention and control groups using Student's t-tests. A false discovery rate (q) will be calculated to reduce false positives with a cut-off point < 0.1.

For the extraction of bacterial DNA from faeces, the commercial QIAamp Stool Mini Kit (Qiagen, Venlo, The Netherlands) will be used. The quality and quantity of the extracted DNA will be spectrophotometrically checked (NanoDrop ND-100). The variable region V4 515F-806R of the 16S rRNA gene will be amplified using specific s-oligonucleotides, by PCR. A second amplification will then be performed using barcode oligonucleotides. The purified PCR product will be sequenced on illumina's MiSeq platform, and the protocols to be followed will be those recommended by the manufacturer. Data analysis. The analysis will be carried out with the QIIME2 v.2019.4 program. The data will be filtered with the q2-dada2plugin implemented in the R software (DADA2 method), obtaining the corresponding ASV (Amplicon sequence variance) correspondents. The taxonomic assignment will be determined with respect to the GreenGenes database (v.13.8). Both alpha diversity (Shannon index) and beta diversity (Unifrac index) will be determined. For the detection of differences in taxonomic composition, the ANCOM method implemented in QIIME2 will be used. A prediction of the metabolic functions of the metagenomes will also be made using the PICRUSt2 tool.

For all these analyses, statistical software such as SIMCA® (Umetrics, Umea, Sweden), Stata and R will be used. Artificial intelligence methods, such as ARM (association rule mining) and GA (generic algorithms) will be used to combine and analyze the phenotypic and metabolomic data in order to understand the most predictive patterns that are associated with better outcomes in this population.

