5.4. Intervention

Participants will be randomly assigned, in a 1:1 ratio, to one of two groups:

Intervention group: Mediterranean diet without red and/or processed meat

They will receive motivation and behavioural support through the use of the mobile application, which will provide them with reminders to self-monitor their changes in eating; while the rest of the clinical care will be usual. After randomization of the patients, the research team will give them more information about the use of the mobile app, with specific

indications to avoid red and processed meat in the context of a healthy Mediterranean dietary pattern, taking into account the key elements proposed in the dietary guidelines for CVD prevention. The app will provide details of Mediterranean diet recommendations, as well as recipes, tips and alternatives to replace meat when cooking at home or eating out. Participants will record their daily diet through the mobile application, during the first and last week of the intervention. The rest of the clinical care will be usual.

Control group: Mediterranean Diet

Similarly, the control group will be helped to download and use the mobile application, although they will only have access to a restricted version of it, by which they will receive brief and general information to maintain a healthy lifestyle following the general guidelines on the Mediterranean diet (without specific recommendations to reduce red and processed meat). Participants will also record their daily diet through the app, during the first and last week of the intervention. The rest of the clinical care will be usual.

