5.7. Data analysis

Sample size

A recent randomized, controlled, peer-to-population trial testing similar dietary approaches to reduce SFA intake showed a long-term change in LDL-C of approximately 15 mg/dL (SD26).¹⁹ If 78 participants are recruited in each group ($n = 156$), it is expected to detect a minimum difference of 15 mg/dl between the intervention group and the control, with a power or detection capacity of 90%, an error $\alpha = 0.05$ and a dropout rate of 20% using intention-to-treat analysis, so the final sample size includes an additional 20% of participants to mitigate dropouts.

Statistical analysis of primary and secondary outcomes

Baseline characteristics will be summarized in descriptive statistics in each study group, statistical analysis will be performed with STATA IC 16.0 software (College Station, TX: StataCorp LLC 2019). Descriptive statistics will be presented with standard deviation (SD) and 95% confidence intervals. Continuous variables will be presented as mean and standard deviation unless the use of the median and interquartile range is necessary; Categorical variables will be expressed as frequencies and percentages.

Efficacy results will be analysed by intent to treat, i.e., all participants will be assessed according to the group to which they are randomly assigned, regardless of their adherence. The analysis of effectiveness measures will use data from all participants for whom a baseline and monitoring measure exists. A linear regression model will be used to calculate the difference in measures with 95% confidence intervals, with adjustment of the initial values of the dependent variable and the place of recruitment. Before the analysis, the assumptions of linear regression, specifically homoscedasticity and the normality of the residual distribution, will be explored. Where these assumptions are not met, appropriate non-parametric analyses shall be used. The sensitivity of the results to confounders due to

differences in baseline characteristics will also be examined. A second sensitivity analysis will use the techniques of "baseline observation carried forwards" (using the initial measure of the variable) and "multiple imputation" (using information about the assigned group and the characteristics of the participants) to impute missing values in the variables of the main outcome. An exploratory analysis of subgroups of results will be carried out according to sociodemographic characteristics.

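### Section 5.8.4 puts variable selection before the responder classifier and fixes no validation, so noise can look predictive unless response-driven selection is repeated inside resampling

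*Protocol*

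**What the plan says.** Section 5.8.4 lists the omics analysis as a sequence. Variables and subject groups are chosen, phenotypic sets are formed, the response to the intervention is examined within each set, and metabolite networks are identified. Everything found is then integrated with genetic algorithms. The closing bullet puts its aim in these words: "once the interesting variables derived from each of the previous approaches (phenotype, microbiota and metabolomics) have been identified, to incorporate them all together". The product is to be a model that sorts patients into good and bad responders.

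The same section later adds association rule mining and genetic algorithms, applied to the phenotypic and metabolomic data "in order to understand the most predictive patterns that are associated with better outcomes in this population". Section 5.8.2 gives the scale of the search: "Non-targeted approaches are used to simultaneously measure hundreds/thousands of metabolic traits". Microbiota taxa come on top of that.

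The one guard against false positives is a false discovery rate with a cut-off of q < 0.1. It follows the tests of time, group and their interaction and the baseline comparisons. The text does not attach it to the rule mining, the genetic algorithm or the classifier. The protocol describes no external cohort, training and test split, cross-validation or permutation test for the model.

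**The concern.** When a few variables are picked from many because they go with the outcome, and a model is then fitted to them in the same patients, the outcome has already shaped the inputs. The fit looks good even if no variable carries information. Cross-validating only the final model does not repair this, because each left-out patient helped to choose the variables. The written order presents selection as finished before modelling begins, so last-step cross-validation is the repair an analyst would naturally reach for.

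At stake is whether a responder classifier, and the patterns said to predict benefit, can be believed. The Background expects the lipid, metabolomic and microbiota work to contribute to dietary guidelines, and the Dissemination plan foresees a paper on the metabolomic results.

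**Working it through.** **1. Number of patients.** Section 5.7 takes a "long-term change in LDL-C of approximately 15 mg/dL (SD26", 90% power, alpha 0.05 (two-sided assumed) and "a dropout rate of 20% using intention-to-treat analysis".

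- Normal approximation: n per arm = 2 × (1.960 + 1.282)² × (26/15)² = 2 × 10.51 × 3.004 = 63.1, so 64.
- t-based calculation: 64.1, so 65 per arm.
- Adding 20%: 65 × 1.2 = 78 per arm, 156 in total. This reproduces the plan: "If 78 participants are recruited in each group ($n = 156$), it is expected to detect a minimum difference of 15 mg/dl".
- Completers: 78 × 0.8 = 62.4, about 62 per arm and 124 in all.

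Section 5.8.4 does not say whether the classifier uses one arm or both, so n = 156, 124 and 62 were all tried.

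**2. Simulation on noise.** There were 200 runs per setting, with independent standard normal traits unrelated to a 50:50 responder label. Assumed trait counts were 200, 1,000 and 5,000. The top 10 or 20 traits by t-test against response entered a ridge linear classifier, w = (X'X + I)⁻¹X'y on centred data. AUC is the probability that a responder scores above a non-responder; its true value here is 0.50. It was computed on the same patients, by 5-fold cross-validation of the final model only, and by 5-fold cross-validation with selection repeated in each fold.

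Mean AUC, selection using response (range over trait counts and number kept):

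| n | Same patients | Only last step cross-validated | Selection inside folds |
|---|---|---|---|
| 156 | 0.81-0.96 | 0.76-0.91 | 0.49-0.51 |
| 124 | 0.84-0.98 | 0.77-0.93 | 0.50 |
| 62 | 0.93-1.00 | 0.84-0.97 | 0.49-0.51 |

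The largest between-run SD was 0.11, so the simulation error of any mean is at most 0.11/√200 = 0.008.

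**3. Selection that ignores response.** Ten or 20 noise traits were taken without looking at the label.

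| n | Same patients (10 / 20 traits) | Last step cross-validated (10 / 20 traits) |
|---|---|---|
| 124 | 0.66 / 0.73 | 0.50 / 0.51 |
| 62 | 0.72 / 0.83 | 0.50 / 0.50 |

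Here same-patient performance is still inflated, but cross-validating the last step is enough.

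**4. A false discovery gate on response.** If traits had to pass Benjamini-Hochberg q < 0.1 against response, at least one noise trait would pass in only about 4-14% of runs.

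**5. Sensitivity.** A separate simulation (100 runs, 10-fold cross-validation, n = 125, 1,000 traits, 10 or 20 kept) gave 0.89/0.95 on the same patients and 0.84/0.88 with only the last step cross-validated. A sparser case (300 traits, 5 kept) gave 0.78 and 0.74, against 0.51 with selection nested. The size moves with the assumptions; the pattern does not.

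**The case against.** The strongest reply is that the protocol commits no stated error. It does not say that selection uses all patients, or that performance will be judged on the patients used for selection. The order it gives could be carried out inside training folds, and a validation scheme for an exploratory model may sit in an analysis plan that is not shown. A reader might infer from 5.8.4 that noise will look highly predictive. The text does not support that: it is silent on where performance is measured, and it promises no AUC or accuracy.

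Secondly, several named methods are not stated to use the responder label: principal components, the multiblock analysis separating arms and time points, the time and group tests with q < 0.1, and ANCOM. For these, step 3 shows that cross-validating the last step suffices. It would therefore be wrong to say that such cross-validation always fails. The genetic algorithm is also described within the integration step, so it is not clearly a prior filter.

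Thirdly, the guideline and publication passages concern the project's results in general and do not mention the classifier.

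All of this stands and limits the point to a conditional one. It does not remove it. Response is examined within phenotypic sets before the final step, and the rule mining and genetic algorithm look for patterns tied to better outcomes, so response-driven selection is a plain reading. The q < 0.1 rule would help if it applied to that search, but the section does not apply it there. The complaint is also not merely that validation goes unmentioned: the written sequence steers towards a repair that fails when selection uses response.

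**Conclusion.** The point holds in conditional form. Section 5.8.4 fixes selection before modelling in one cohort with many more traits than patients, and ties no validation or error control to the classifier. With 62 to 124 patients, same-patient AUC on noise is about 0.66-0.83 if selection ignores response and 0.84-1.00 if it uses response. In the latter case, last-step cross-validation still gives about 0.77-0.97, against 0.49-0.51 when selection is nested.

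These figures rest on assumed trait counts, number kept, a 50:50 responder share, a linear classifier and independent normal traits; correlated traits, usual in metabolomics, were not tested. The response-blind figures also assume that the chosen traits are unrelated to responder status.

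A reader might take this as a threat to the trial's main result. It is not: it touches only the exploratory responder model and leaves the LDL-C comparison as it is.

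**What to change.** Amend the last bullet of 5.8.4 as follows.

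- Every selection or search step that uses the response (rule mining, the genetic algorithm, any response-based filter or choice of phenotypic set) is repeated inside each training fold. Alternatively, the whole pipeline is tested on held-out patients.
- Only out-of-fold or held-out performance is reported, with a permutation test of that whole pipeline. The test is needed because even nested AUC on noise had a between-run SD of 0.10-0.11 at n = 62, so a single value near 0.60 would be unremarkable.
- Patterns selected on the full data are labelled descriptive.

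Steps that do not use the response, such as principal components and the arm and time contrasts, need not be nested.

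The cost is one paragraph, computing time and a lower but honest reported accuracy. No new data are needed.

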5. METHODOLOGY

5.1. Experimental design

The CADIMED study is a randomized, controlled (two parallel arms) dietary intervention study, where the effect of an eight-week behavioural intervention consisting of a Mediterranean dietary pattern with elimination of red and processed meat will be evaluated, compared to the general advice for decreasing SFA intake in patients with elevated LDL-C.

To this end, 156 patients ≥ 18 years of age with dyslipidaemia and who express their desire to improve their diet and reduce the risk of CVD will be recruited. The study will be registered in ClinicalTrials.gov and a Good Clinical Practice and Trial Quality Assurance strategy will be established (see section 11 for other ethical and legal considerations).

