5.2. Study population

Inclusion criteria:

- 1) Signed informed consent;
- 2) Age ≥ 18 years to ≤ 75 years;
- 3) Indicated to start lifestyle intervention based on recent values (e.g., last 3-6 months) of LDL-C ≥ 116 mg/dL and < 190 mg/dL; as long as pharmacological intervention has not been advised and started (*ESC/EAS Guideline, Rev Esp Cardiol. 2020*);
- 4) Device access (e.g. *smartphone, tablet*) with internet and digital skills for the use of the mobile application;
- 5) Motivation and willingness to be assigned to any of the groups to improve their diet, as well as commitment to carry out the assigned protocol.

Exclusion criteria:

- 1) Patients with familial hypercholesterolemia and/or on treatment with lipid-lowering drugs (including statins, ezetimibe, PCSK9 inhibitors, fibrates, bile acid chelators, Omega 3 fatty acids, nicotinic acid/Vit B3), dietary supplements or functional foods for the treatment of dyslipidaemia (plant sterols, monacolin, red rice yeast, fibre supplements 3-10g (plantago), policosanol, berberine and soy protein/lecithin) in the last 3 months;
- 2) Cardiovascular risk that makes the use of drugs necessary, for example, in patients with recent and/or established CVD; type 1 and 2 diabetes;
- 3) Uncompensated thyroid function disorders; relevant comorbidities (including liver failure and cholestasis, chronic kidney disease, Cushing's syndrome, nephrotic syndrome, obesity grade III – BMI > 40 kg/m²); cancer; psychiatric disorders and/or that in the opinion of the researcher makes it difficult to comply with or follow up on the study;
- 4) Excessive alcohol consumption: > 40 g/d (4 UBEs/day) in men and $> 20-25$ g/d (2-2.5 UBEs/day) in women (*Ministry of Health, July 2020*)

- 4) Pregnancy, lactation, perimenopause (amenorrhea <1 year), and women who change, start, or end hormonal contraceptive treatment during the study;
- 5) Participation in other research or dietary pattern (e.g. vegetarian and vegan) that could interfere with the demands of the study;
- 6) Failure to provide informed consent or failure to complete the initial assessment.

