In addition, help will be offered to access and use a mobile application (designed especially for the study) to start collecting data on diet. The app will include each patient's unique code and a built-in diet questionnaire that will need to be completed at least twice a week (ideally every day), during the first and last week of the intervention to obtain valid measures of usual intake. In addition, a questionnaire on the frequency of food consumption during the previous 4 weeks will be completed to assess the eating pattern.

4) Blood samples: the nurse in charge of the project will take blood samples during the 1st initial visit and at the end of the follow-up of each patient, with an overnight fast of 8 hours. The samples will be processed in the laboratory of the Virgen de las Nieves Hospital for subsequent analysis in the same hospital; in addition to the transfer/storage of the remaining samples in our laboratory of the Institute of Nutrition and Food Technology (INYTA) (details on page 11-12).

5) Stool samples: stool samples will be taken at the beginning and end of follow-up for which patients will be provided with the necessary material and instructions for collection (e.g. taking antibiotics) and storage of the samples. The samples will be delivered to the research team during the 2nd initial visit for processing and storage in our laboratory at the Institute of Nutrition and Food Technology (INYTA).

6) Randomization and assignment of the intervention group. During the 2nd initial visit, and once it has been confirmed that patients meet all the inclusion requirements, the intervention group will be randomly assigned and the corresponding explanation to the patient will be carried out.

Table 1. Data collection at CADIMED study visits

	Evaluation Preview	1st visit initial	2nd visit initial	Visit End
a. Pre-selection questionnaire (via telephone)	x			
b. Signed consent		x		
c. General questionnaire (demographics, lifestyle)		x		x
d. Anthropometric measurements, blood pressure, clinical data		x		x
e. Physical activity questionnaires, 24-hour food and diet patterns		x	x	x
f. Blood sample collection		x		x
g. Stool sample collection			x	x
h. Randomization and Intervention Allocation			x	

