5.6. Definition of variables: main and secondary results

With the determinations and measurements derived from the CADIMED study, it is proposed to investigate the following results (comparing the intervention group and the control group):

- 1) Main results: changes in LDL-C and fatty acid profile in erythrocytes after 8 weeks of intervention
- 2) Secondary outcomes:
 - a. Changes in other metabolites derived from lipid and metabolomic profile analysis, including circulating fatty acids, HDL-C, total cholesterol, triglycerides, and endogenous and exogenous metabolites related to cardiovascular risk and meat consumption (e.g., TMAO, etc.);
 - b. Changes in other related markers of cardiovascular risk, including biomarkers of inflammation and endothelial damage, insulin resistance, and diabetes (glucose, insulin, HbA1c, C-reactive protein, IL6, TNF-alpha), blood pressure, weight, and body and waist mass index;

- c. Changes in the gut microbiota and derived metabolites
- d. Changes in dietary intake (measured by 24-h recall): SFA intake, total energy intake, total fat, sugar, fiber, salt, general dietary patterns, red and processed meat consumption.
- e. Changes in other lifestyle-related factors: collected through physical activity, smoking, and alcohol questionnaires

3) **Evaluation of the process**: analyses of both quantitative and qualitative measures will be included to understand whether the intervention has worked and through which processes. These measures include: the rate of recruitment of volunteers and the rate of patients completing the study; acceptance of the intervention through questionnaires at the end of follow-up; the use of the mobile application to carry out changes in the diet as well as the self-monitoring of intake; measures that evidence the contamination of the control group; changes in patients' ability and knowledge about diet, SFA, and cardiovascular disease.

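### Section 5.8.4 ends by classifying individuals as good or bad responders, which two parallel arms with one value before and one after cannot show, and the step is not tied to a between-arm contrast

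*Protocol*

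**What the plan says.** Section 5.8.4 sets out a stepwise data-mining process. It selects variables, forms phenotypic sets without using the omics data, examines the intervention-associated response in each set, and identifies metabolite networks. Its last step takes the variables found earlier and proposes "to incorporate them all together for the construction of a predictive model that allows the classification of good and bad responders to treatment". The closing paragraph of the section adds that association rule mining and genetic algorithms will combine phenotypic and metabolomic data "in order to understand the most predictive patterns that are associated with better outcomes in this population".

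The same section also plans group-level comparisons: AMOPLS to separate the arms before and after the intervention, and tests of time, group and time by group. None of these is named as the basis of the responder model. The section gives no definition of a responder, no outcome on which response is judged, no cut-off, and no statement on baseline adjustment.

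The design is fixed elsewhere. Section 5.1: "The CADIMED study is a randomized, controlled (two parallel arms) dietary intervention study". Section 5.3: the project nurse "will take blood samples during the 1st initial visit and at the end of the follow-up of each patient", and Table 1 shows the same two blood draws. There is no crossover, repeated period or replicate baseline. Section 5.2 bases eligibility on an earlier LDL-C: "based on recent values (e.g., last 3-6 months) of LDL-C ≥ 116 mg/dL and < 190 mg/dL".

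**The concern.** To call someone a good responder to treatment is to say that this person's outcome differs from what it would have been on the control advice. A parallel trial never observes that second outcome for anyone. It estimates the mean difference between arms and, through interactions, how that mean difference varies with baseline features. It does not show which individuals benefited.

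A classifier trained on change within treated participants learns predictors of change. Some of these are purely statistical: a person whose baseline reading happened to be high will tend to show a larger fall on any regimen. Any metabolite or taxon correlated with baseline LDL-C inherits that association. The protocol presents this model as the step that integrates the phenotypic, microbiota and metabolomic work. A panel reported as identifying responders could be believed although nobody responds differently.

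**Working it through.** **Inputs from the protocol (section 5.7).** Effect 15 mg/dL, SD 26, power 90%, alpha 0.05 (two-sided assumed), 20% dropout, 78 per group. The protocol does not say outright whether SD 26 is that of change or of level; it is read here as the SD of change.

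**The plan's own figure.** n per arm = 2 × (1.96 + 1.28)² × 26² / 15² ≈ 63, or 64 to 65 after rounding and the t correction. 65 × 1.2 = 78, and 64 / 0.8 = 80. The stated 78 reproduces within two patients, so 15 and 26 are the figures in use. With 20% dropout, 156 × 0.8 ≈ 125 patients are analysed.

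**Step 1: share labelled good responder when everyone has the same effect.** Take a cut-off of c mg/dL fall (an assumption; the protocol gives none).
- Intervention: Φ((15 − c)/26). Control with zero mean change: Φ(−c/26).
- c = 15: 50% and Φ(−0.577) = 28%.
- c = 10: 58% and 35%. c = 20: 42% and 22%.

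The 50% follows simply from placing the cut at the assumed mean. The 28% is more informative: more than a quarter of people with no treatment effect would pass.

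**Step 2: dependence of change on baseline.** With equal variances and baseline-to-final correlation ρ, corr(baseline, change) = −√((1 − ρ)/2).
- ρ = 0.5: −0.50. ρ = 0.8: −0.32.
- With the cut at the mean change, the share of good responders above the median baseline is 1/2 + arcsin(|r|)/π. This is 67% against 33% below the median for ρ = 0.5, and 60% against 40% for ρ = 0.8.
- Controls with no effect show the same gradient: 42% against 14% for ρ = 0.5, and 37% against 20% for ρ = 0.8.

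**Step 3: how well baseline LDL-C alone predicts the label.** This is a simulation with a constant 15 mg/dL effect and a 15 mg/dL cut. Selection is on an earlier reading of 116 to below 190, as in section 5.2, followed by a fresh baseline reading. The population mean (135 or 150), between-person SD and within-visit SD are assumptions.

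| Between-person SD | Within-visit SD | SD of change | AUC, intervention | AUC, control |
|---|---|---|---|---|
| 18 | 12 | 17 | 0.70 | 0.72 |
| 18 | 18.4 | 26 | 0.75 | 0.76 |
| 25 | 12 | 17 | 0.67–0.68 | 0.69 |
| 25 | 18.4 | 26 | 0.72 | 0.73 |

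If the window is instead imposed on the baseline sample itself, the AUC is 0.59 to 0.68 (intervention) and 0.60 to 0.69 (control).

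The control column is the key one. The prediction is as good where there is no treatment effect, so it cannot be a prediction of response to treatment.

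**Step 4: baseline-adjusted label.** If the label is taken from the residual of final on baseline LDL-C, the AUC of baseline falls to 0.50. The participants still split into good and bad although all have the same effect. That split is random variation.

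**Step 5: where the mean shift falls.** With selection on an earlier value, the mean change from baseline to final in untreated people is about zero, because the shift caused by selection occurs before the baseline sample. What remains is the individual-level dependence in steps 2 and 3.

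**The case against.** The protocol defines no responder, so the choice of outcome, cut-off and adjustment may belong to an analysis plan that is not shown. A reader might infer that the model will label regression to the mean as response. The protocol does not support that. Section 5.7 adjusts its efficacy models for the baseline value, a similar label here is plausible, and step 4 shows that it would remove the baseline artefact. This stands, and the regression-to-the-mean result is therefore conditional on a raw-change label. It does not rescue the classification, because no definition of the label supplies the missing outcome on the other regimen.

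Between-arm thinking is not absent from section 5.8.4. The time-by-group test and AMOPLS compare arms, a false discovery rate is applied, and the step on phenotypic sets comes close to a subgroup-effect analysis and feeds the last step. This also stands, and it makes the repair easier. But these work on groups, and the text does not say that the responder model is fitted as a contrast with control.

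A reader might also infer that the trial's main result is at risk, or that advice would be targeted by this model. Neither follows. Responder classification is not an objective in section 4.2 or an outcome in section 5.6, whose main results are "changes in LDL-C and fatty acid profile in erythrocytes after 8 weeks of intervention". Section 6 envisages advice at population level, not advice guided by a responder panel.

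**Conclusion.** The concern holds for the last step of section 5.8.4. Individual response to treatment is not identifiable from two parallel arms with one measurement before and one after, and the responder model is not tied to the control arm. This is a flaw in the stated aim, not a detail left for later.

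The size of the distortion depends on the undefined label. With raw change, baseline LDL-C alone would look moderately predictive (AUC about 0.67 to 0.75 with selection as in section 5.2) in a trial where everyone benefits equally. With a baseline-adjusted label that artefact disappears, and what is classified is noise. The figures rest on an assumed 15 mg/dL cut, LDL-C as the outcome, SD 26 read as the SD of change where it is used, and the assumed variances shown.

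It would be wrong to conclude that the trial can say nothing about differing effects: with a control arm, treatment-by-feature interactions can be estimated. The step is exploratory and the primary LDL-C comparison is untouched, so this is a change that should be made rather than one on which the trial depends.

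**What to change.** Restate the last step of section 5.8.4 as an exploratory model of final LDL-C (or another named outcome), fitted in both arms together:

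final value = baseline value + group + feature + group × feature.

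- Build on the phenotypic-set step by reporting the between-arm difference within each set.
- Call a feature predictive of response only if its interaction with group holds in cross-validation. Call all other associations with outcome prognostic.
- Apply the same rule to the patterns from association rule mining and genetic algorithms.
- Do not report individuals as good or bad responders.

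This changes analysis wording only; the data, visits and samples stay as planned. The cost is a more modest claim with low power. For a feature that splits about 125 analysed patients in half, the standard error of the interaction is about 4 × 26/√125 = 9.3 mg/dL. At 90% power and a single two-sided test at 0.05, the detectable interaction is about 3.24 × 9.3 = 30 mg/dL, twice the assumed treatment effect. Baseline adjustment lowers this somewhat, and multiplicity across many features raises it. The step may find nothing, and the protocol should say so.
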